All study personnel will have completed the mandatory CITI human subjects research training before commencing any study-related activities.

The informed consent form for this study has been created by the NYU School of Medicine Office of Science and Research in accordance with Federal guidelines, including the Health Insurance Portability and Accountability Act (HIPAA).

CHW Treatment Participants

All potential treatment participants will receive a copy of the study consent form by the CHW. The format of the consent form consists of a 1-page consent signature form with an accompanying brochure fully detailing all components of the full informed consent (See Consent Brochure and Consent Signature Page for CHW Intervention and Key Information Sheet). This layout is more appropriate for clinic-based and community-based recruitment. First, based on our experience in previous community-based studies, community members were discouraged by a multiple-page consent form, and we expect the same in a clinic setting. Even though this format provides the same exact information as the standard consent form, we expect that it will be less intimidating for participants who are learning about the study in a community-based recruitment atmosphere.

Consent processes will be conducted in a manner that maximizes confidentiality and privacy and allows questions to be asked. Eligible patients demonstrating interest in participating in the project will meet with a study team member who will explain the intervention and consent form and invite them to sign a consent form. Consent will be obtained in a closed room, on a one-on-one basis. Participants are free to withdraw from participating in the study at any time without repercussions. Participants will be advised during the consent process that they have the right to withdraw entirely and that their refusal will not jeopardize their relationship with their CHW or primary care physician.

Provider Surveys

A Waiver of Documentation of Consent is being requested for participants of the Provider Survey for this study (See Application for Waiver of Documentation of Consent for Provider Survey and Key Informant Interview). This request is being made because the consent form, if collected, would require names to be collected and in doing so would be the only record linking the subjects name to the research. The study will invite participation by email to complete the online survey, who will give implied consent if they click on the hyperlink to complete the survey, or if participants wish to complete a paper-based survey, the study team will obtain verbal consent (See Invitation Script and Elements of Informed Consent for Provider Survey). The consent email will be sent out by study staff. The study offers a hyperlink for participants if they agree to participate in the study. It will state clearly that participation is completely voluntary, and

there is no penalty in declining to participate in the study. Participants will be informed they are free to withdraw from participating in the study at any time without repercussions.

Key Informant Interviews

A Waiver of Documentation of Consent is being requested for participants of the Key Informant Interview for this study (See Application for Waiver of Documentation of Consent for Provider Survey and Key Informant Interview). This request is being made because the consent form, if collected, would require names to be collected and in doing so would be the only record linking the subjects name to the research. Verbal consent will be obtained prior to start of the interview, but we will not collect any personal information or identifiers. No names of individuals will be recorded or appear in interview notes. Participants will be free to withdraw from the interview at any time without repercussions. Participants will be provided with an invitation including the elements of the written consent as well as contact information for the study PI. Verbal consent will be obtained from the key informants prior to beginning the interview (See Verbal Consent Script for Key Informant Interview). The language in the recruitment and verbal consent materials for NYU employees which details their risks (coercion, invasion of privacy or loss of confidentiality) and specific protections as a vulnerable population will always apply specifically because they are the individuals involved in the methods under study. This language does not apply to research subjects who are involved in the interviews who are not NYU employees.

Focus Groups

A Waiver of Documentation of Consent is being requested for the random sample of participants previously enrolled in the CHW intervention invited to participate in the Focus Group (n=50) (See Application for Waiver of Documentation of Consent for Focus Group). This request is being made because the consent form, if collected, would require names to be collected and in doing so would be the only record linking the subject's name to the focus group component (meaning that they were part of the random sample of treatment group participants who also participated in the focus group, which is a smaller sample than that of the CHW intervention. This will be a one-time anonymous audio-recording with no follow-up; no names or identifying information will be collected at the time of the focus group. Verbal consent will be obtained prior to start of the focus group, but we will not collect any personal information or identifiers. No names of individuals will be recorded or appear in notes. Participants will be free to withdraw from the focus group at any time without repercussions. Participants will be provided with an invitation including the elements of the written consent as well as contact information for the study PI. Verbal consent will be obtained from the focus group participants prior to beginning (See Verbal Consent Script for Focus Group).

B. Subject Capacity

We anticipate that all subjects will have the capacity to give informed consent. Language barriers will be minimized by having data collectors who speak Bengali, Urdu, and Punjabi and translated consent forms for the CHW Intervention (to be translated upon approval of the English version and submitted to IRB for review and approval via a modification).

C. Subject/Representative Comprehension

To determine that the subject or his/her authorized representative understood the information presented, they will be given opportunity to ask questions before giving consent to participate. They can also choose at that time not to be in the study. The individuals authorized to obtain consent will do so by presenting to the subjects the consent form and will verbally read along with the subject and explain the study. The individuals will explain the purpose of the study, the procedures, possible risks and anticipated benefits, that it is voluntary, and how to withdraw if they choose to at a later time. Limited English speaking individuals will be given a translated consent form, and Bengali/Urdu/Punjabi-speaking personnel will obtain consent from them.

D. Debriefing Procedures.

Information will not be withheld from the subjects related to their participation in the study.

E. Consent Forms. Eligible treatment patients will be consented and enrolled to participate in the study (see Consent Brochure/Signature Page for CHW Intervention).

F. Documentation of Consent

Informed consent will be documented by the use of a written consent brochure/signature page to be signed and dated by the subject or the subject's legally authorized representative at the time of consent (See Consent Brochure and Consent Signature Page for CHW Intervention) for all those participants enrolled in the CHW intervention. Individuals authorized to obtain consent will read the consent form to the subject or the subject's legally authorized representative, and the subject or representative will be given adequate opportunity to read it and clarify questions before it is signed. The subject will receive a copy of his/her signed consent form. A translated written consent form will be used for non-English speaking subjects, depending on their preferred language. The informed consent will outline elements of the EHR data collection, CHW group education, one-on-one counseling and survey data collection.

Baseline surveys will also be conducted by Emory study staff with participants within two weeks after consent. The same survey will be completed with intervention participants approximately six months after the start of intervention to evaluate the effectiveness of the CHW intervention, the CHW Intervention 6-month survey will be completed at the last education session.

A waiver of consent will be submitted to obtain Emory and NYU EHR data to characterize to obtain the data points characterizing South Asians in these two areas.

G. Costs to the Subject

There are no costs to participate in this study. Any doctor visits and laboratory tests, including the HbA1c test, are part of standard of care.

H. Payment for Participation

Participants will need to travel to the clinic or community-based sites to participate in the group-based health education sessions. Participants will receive compensation for their time, effort, and travel. Participants will receive \$10, in the form of a gift card upon completion of each of the health education sessions. Small prizes such as pedometers will be given at educational sessions. The participants will also receive compensation of \$25 for the completion of the final survey. Participants of the focus groups will receive a \$10 gift card.

XI. APPENDIX

- A. Recruitment Letter for CHW Intervention
- B. Script for Telephone Screening for CHW Intervention
- C. Telephone Screening Form for CHW Intervention
- D. Participant Survey Baseline
- E. Participant Survey Followup
- F. Provider Survey(baseline and followup)
- G. Key Informant Interview Guide(baseline and followup)
- H. Consent Brochure and Consent Signature Page for CHW Intervention
- I. Key Information Sheet
- J. Key Information and Verbal Consent for Provider Survey
- K. Key Information and Verbal Consent for Key Informants
- L. Application for Waiver of HIPAA for Telephone Screening

- M. Application for Waiver of Documentation of Consent for Provider Survey and Key Informant Interviews, and EHR Characterization
- N. Text Message Script
- O. Action Plan
- P. Progress Note
- Q. One-on-One Form #1
- R. One-on-One Form #2
- S. Encounter Report
- T. Recruitment Flyer
- U. Focus Group Topic Guide (Template and Site-Specific)
- V. Interview Guide – Implementing CHW (Template and Site-Specific)
- W. Interview Guide – NYU CHW (Template and Site-Specific)
- X. Key Information and Verbal Consent Script for Focus Group
- Y. Application for Waiver of Documentation of Consent for Focus Groups

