The proposed project takes place in two parts: part one builds upon the evidence base of the effectiveness of culturally tailored CHW interventions and proposes to replicate and scale a CHW intervention. A critical need exists to tailor, translate, and disseminate evidence-based CHW interventions to maximize impact in ameliorating co-morbid CVD disparities. Part two describes the variation of cardiovascular disease risk across South Asian populations in the US derived from electronic health records. Our study takes a first step towards filling this gap in the literature, by characterizing the burden of disease among two South Asian communities. This project will facilitate bidirectional collaboration by building this data set across two sites in the United States. This will complement ongoing work by the investigative team to replicate an efficacious intervention program delivered in NYC in Atlanta.

B. Study aims

Specific Aim 1: Provide research training, technical assistance, and capacity-building to community and clinical sites in Georgia for implementation of culturally tailored, evidenced-based CHW programs to improve HTN and diabetes management for South Asians.

Specific Aim 2: Use a multi-theoretical framework to test the effectiveness of a CHW-led intervention compared to usual care among South Asian individuals with diabetes and uncontrolled HTN in Atlanta.

Specific Aim 3: Apply RE-AIM and CFIR frameworks to delineate factors influencing reach, appropriateness, fidelity, adoption, and maintenance of the intervention within clinical and community settings to optimize intervention replication.

Sub-Aim3a: Serve as a national information and dissemination resource in the adaptation of evidence-based strategies to reduce geographic disparities in HTN and diabetes across Asian American groups.

B. Study Outcomes

Phase 1: See below: this is the planning and technical assistant phase of the proposal.

Phase 2: The primary outcome of interest is proportion of patients that achieve BP control, defined as less than or equal to 130/80 mmHg, at 6 months. The secondary outcomes of interest include changes in HbA1c, SBP and DBP, and BMI at 6 months.

Phase 3: The outcomes for the provider surveys, informant surveys, and EHR will be descriptive data to inform with to facilitate the development of intervention strategies within the larger healthcare system

III. STUDY DESIGN

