A randomized control design will be used to test the efficacy of the CHW intervention to improve HTN control among South Asian individuals with diabetes in Atlanta. The intervention will recruit participants from three clinical sites in Atlanta, GA: 1) The Emory Family Medicine Clinic is located in North Atlanta and serves approximately 1,200 unique South Asian patients annually; 2) Grady Clinic at Brookhaven is a safety net county clinic that sees a high volume of low-income South Asians (approximately 6,000 per year; 3). The Shifa Free Clinic is a community-based free clinic coordinated by the Islamic Circle of North America, Atlanta branch, to serve uninsured and under-insured South Asians in Georgia.. On average, they see 200 unique South Asian patients per month at each site. Both Emory Family Medicine Clinic and Grady Clinic utilize EHR systems which will be used to generate lists of eligible patients for the intervention. Shifa Clinic is currently transitioning to an EHR system, thus patient data will be electronically accessible for patient recruitment and follow-up outcome data. Each of the sites has expressed interest and commitment to participating in the study. The community centers will not be engaged in research, all consenting and procedures will be completed by Emory study staff.

We also anticipate enrolling participants from community-based recruitment with the CHWs referring participants that they meet at South Asian community events and advertising the study. The proposed research design is a modified stepped wedge design, whereby 2 groups will implement the intervention in phases. The time prior to the intervention will serve as the comparison group. Enrolled patients will be randomized to treatment (Group A) and wait-list control (Group B) groups within each site.

There are five primary research groups for this study: 1) 326 treatment participants who will receive the CHW intervention; 2) 326 control participants who may receive the CHW intervention as a point of service at a later point; 3) 10 subjects who will participate in provider surveys; 4) 25 subjects who will participate in qualitative key informant interviews; 5) a retrospective EHR review of characteristics of South Asians seen at Emory Healthcare and NYU hospital system between 2014 and 2019; and 6) 50 subjects who will participate in focus groups.

B2. CHW Component:

1. Data collection and consenting with treatment participants

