After letters from the provider practices of the 3 participating clinical sites have been mailed to eligible patients or they have been notified of the study by their provider, CHWs will contact patients via mailing and phone calls to invite them to enroll into the intervention. CHWs will call patients a maximum of ten times over a two-week period at varying times of day to invite them to enroll into the study. In addition, list of eligible treatment participants will be shared with primary care physicians who will be encouraged to refer patients to contact CHWs during routine visits. CHWs will also table at primary care provider (PCP) clinics and community events to enhance recruitment and enrollment. During the recruitment call, CHWs will conduct a brief screening to confirm eligibility (see Screening Form). If eligible, patients will be invited to complete an in-person consent form (See Consent Brochure and Consent Signature Page for CHW Intervention) and survey (see Participant Survey) that assesses baseline demographic and logistical information, such as preferred language and session availability. Participants must sign a consent form in order to participate, which will be administered by the CHW or bilingual study coordinator.

Surveys will be collected from all participants at baseline and 6 months. Baseline surveys will be conducted by a CHW or bilingual study coordinator immediately following consent. Six-month surveys will be conducted in person by a study staff within two weeks of completion of the CHW coaching component of the intervention. Survey measures will be developed based on their 1) brevity; 2) presence of domains with face validity for Asian American or low literacy communities; and 3) valid psychometric properties, thus enhancing scientific rigor. Survey measures include weight and blood pressure measurements, as well as questions about self-efficacy, medication adherence, and referrals to social services.

Patient-engagement measures: Contact with eligible treatment group participants will be collected in REDCap or on paper-based CRFs, including phone contact attempts, patients' intervention status (declined, enrolled, not reached etc.), completion of intervention activities (such as health education sessions and phone-based health coaching), and completion of data collection, referrals, and intervention activities across sites and CHWs.

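### The consent section puts the six-month survey at the last education session, in month 5, against the schedule's month 6, and the analysis section counts six months from an undefined visit

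*Combined protocol and SAP*

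**What the plan says.** - **Endpoint (II.B, Study Outcomes).** Blood pressure control is "defined as less than or equal to 130/80 mmHg, at 6 months".
- **Where blood pressure is collected (III.B2).** "Surveys will be collected from all participants at baseline and 6 months", and "Survey measures include weight and blood pressure measurements".
- **Survey timing, design section (III.B2).** "Six-month surveys will be conducted in person by a study staff within two weeks of completion of the CHW coaching component of the intervention".
- **Survey timing, schedule (VI.A, CHW Intervention Period).** Session 5, the last of the five sessions listed in IV.A1, is in month 5 and is followed by two calls in that month. The endpoint survey is in month 6.
- **Survey timing, consent section (F. Documentation of Consent).** One sentence gives two rules. It begins "The same survey will be completed with intervention participants approximately six months after the start of intervention" and ends "the CHW Intervention 6-month survey will be completed at the last education session".
- **Controls (VII.A, Control Participants).** They attend Session 1 only, complete baseline and endpoint surveys, and are otherwise not contacted until the treated arm has finished.
- **Analysis (VII.B1, Specific Aim 2).** The outcome is dated six months from an index office visit. The term appears twice there and is defined nowhere in the text available. The model description in the same section refers to the end of the six months.

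**The concern.** Staff cannot follow both the closing clause of the consent section and the schedule in VI.A. The clause sits in an administrative section, but the same sentence says the survey serves to evaluate effectiveness, and the survey is the only blood pressure measurement scheduled for both arms. A rule for its date is therefore probably a rule for the date of the primary endpoint.

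The clause is written for intervention participants and cannot date the control endpoint, because controls have no last session beyond Session 1. If it were applied, treated participants would be measured before their coaching was complete and only if they came to a session, while controls would be measured later at a separate contact. Randomisation does not protect against outcome timing and ascertainment that differ by arm.

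The undefined index visit is a separate gap. Without one stated time zero, an analyst cannot tell which reading is the six-month reading for a given participant.

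**Working it through.** **Convention (an assumption).** The schedule gives months, not dates. I take month k to run from k−1 to k elapsed months.

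**1. Reproduce the plan's call count.** Calls in months 1 to 5 (VI.A): 1 + 1 + 2 + 1 + 2 = 7. This matches the seven calls in IV.A1, so the schedule is a sound reference.

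**2. Coaching still to come at Session 5.** Calls before it: 1 + 1 + 2 + 1 = 5. Calls after it: 7 − 5 = 2, and 2/7 = 29%.

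**3. When each rule places the treated survey.**

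| Source | Elapsed months |
|---|---|
| Consent section, closing clause (Session 5, month 5) | 4 to 5 |
| Consent section, opening of the same sentence | about 6 |
| VI.A (month 6) | 5 to 6 |
| III.B2, coaching ends in month 5 | no later than 5 + 0.5 = 5.5 |
| III.B2, coaching runs to month 6 (IV.A1 lists only a minimum set) | up to 6 + 0.5 = 6.5 |
| VII.B1, end of the six months | 6 |

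The closing clause is early by 6 − 5 = 1 to 6 − 4 = 2 months against the end of the six months. III.B2 and VI.A overlap, so they can be satisfied together. The clause does not fit VI.A. It does not fit III.B2 either, in the ordinary sense of a survey after coaching ends, because two calls remain.

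**4. Possible gap between arms.** Take the intervention as complete at the end of its six-month period, so controls are reached at about 6.
- Closing clause for treated, VII.A for controls: 6 − 5 = 1 to 6 − 4 = 2 months.
- VI.A for treated, VII.A for controls: 6 − 6 = 0 at the least.

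If completion were declared at the start of month 6, the first gap would shrink to between 5 − 5 = 0 and 5 − 4 = 1 month.

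**5. Sample size.** VII.B2 assumes 15% against 35% at six months, two-sided 0.05, 80% power and 10% loss. With pooled proportion 0.25, n = [1.960√(2 × 0.25 × 0.75) + 0.8416√(0.15 × 0.85 + 0.35 × 0.65)]² / 0.20² = (1.200 + 0.501)² / 0.04, or about 72.4, which rounds up to 73 per arm. Then 73 × 1.1 = 80.3, giving 81, or 73/0.9 = 81.1, giving 82. The stated 81 per arm reproduces. Survey timing does not enter the formula beyond the six-month rates already assumed, so nothing here changes it.

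**The case against.** The strongest reply is that this is one stray clause in a consent section. The design, schedule and analysis sections all point to month 6 or the end of coaching, and a sensible team would follow those. That stands as a limit on the consequence, but the clause is still a written instruction that contradicts them.

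Several stronger readings are tempting, and the documents do not carry them:

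- **That the arms will be measured at different times.** This needs the clause to be followed for one arm and the control-contact rule for the other. Under III.B2 or VI.A the gap can be zero.
- **That the survey is certainly the endpoint source.** This is inferred. No section names the source. III.B1 mentions electronic follow-up outcome data for one clinic, VII.A refers to data extracts, and consent covers record data. If the endpoint came from records, the clause would not date it.
- **That community recruits have no index visit.** VI.A brings those who agree to enrol to a clinic for consent and the baseline survey, so a candidate visit exists. The defect is an undefined term.
- **That the power and sampling sections are contradicted.** VII.B2 and VII.B3 mention six-month follow-up but set no visit rule.
- **That different kinds of assessor measure the two arms.** III.B2 gives the six-month survey to study staff, while VII.A has controls surveyed with CHWs. The category can include CHWs: III.B1 says "all consenting and procedures will be completed by Emory study staff", and III.B2 describes the consent form as one "which will be administered by the CHW or bilingual study coordinator".

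**Conclusion.** The closing clause is wrong as written. It conflicts with VI.A, with III.B2 and with the opening of its own sentence, and it places the treated survey 1 to 2 months before the end of the six months, with 29% of the scheduled calls outstanding. Separately, the index office visit in VII.B1 is undefined.

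The consequence is conditional. A gap between arms of roughly 1 to 2 months arises only if the clause is applied to treated participants and the VII.A contact rule to controls. It rests on the month convention, on completion falling at the end of month 6, and on survey blood pressure being the endpoint source. The documents give no time course for blood pressure control, so neither the size nor the direction of any bias can be stated. The contradiction is certain, its effect is uncertain, and it should be fixed because the repair is cheap.

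**What to change.** 1. In F. Documentation of Consent, delete the words that place the survey at the last education session.
2. In VII.B1, replace the index office visit with one date that every participant in both arms has. Randomisation, Session 1, or the clinic consent and baseline visit in VI.A would each serve.
3. State one six-month survey window from that date in III.B2, VI.A, VII.A and VII.B1, and F. It should be the same in both arms and apply regardless of session attendance. Word the control-contact rule so that it allows the survey inside the window.
4. State that the primary-endpoint blood pressure is the survey-visit reading, or name the source actually used.
5. Require a first-wave control's endpoint survey before enrolment in wave 2.

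**Cost.** Wording and scheduling only. Treated participants make an endpoint visit separate from a session, which the month-6 survey in VI.A and the separate final-survey payment (H. Payment for Participation) already imply. The anchor may move the survey slightly. VII.A randomises after Session 1, in month 1 (0 to 1), so six months from randomisation falls at 6 to 7 on the VI.A calendar. That is past month 6, and looser than the III.B2 link to the end of coaching. No sample-size or power figure needs to change.
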